#### **Diabetic ketoacidosis:**

DKA is reportable as an adverse event when the subject reports the following:

- Symptoms such as polyuria, polydipsia, nausea or vomiting, and
- Treatment provided in a health care facility, and
- Diagnosis of DKA made by a health care provider and self-reported by the patient.

Subjects will be instructed on this specific definition of DKA each time information is requested related to this AE.

#### **Serious Adverse Event (SAE):**

In accordance with 21 CFR Parts 803 and 812, a SAE is defined as any untoward medical occurrence that:

- Results in death,
- Is life-threatening,
- Requires hospitalization or prolongation of existing hospitalization,

- Results in persistent or significant disability/incapacity or substantial disruption of the ability to conduct normal life functions,
- Is a congenital anomaly or birth defect, or
- Is considered a significant medical event by the investigator based on medical judgement (e.g., may jeopardize the subject or may require medical/surgical intervention to prevent one of the outcomes listed above).

Medical and scientific judgement will be exercised in deciding whether medical events that may not be immediately life-threatening or result in death or hospitalization, but may jeopardize the subject or may require intervention to prevent one of the other outcomes listed in the definition above, should also be considered serious. A serious adverse event must be reported to the FDA as soon as possible, within a maximum of 15 calendar days.

### **Unanticipated Adverse Device Effect (UADE)**

In accordance with 21 CFR Part 812, an UADE is any serious adverse effect on health or safety or any life-threatening problem or death caused by, or associated with, a device, if that effect, problem, or death was not previously identified in nature, severity, or degree of incidence in the risk assessment, the ICF as well as the protocol, or any other unanticipated serious problem associated with a device that relates to the rights, safety or welfare of subjects. An unanticipated device effect must be reported to the IRB within 5 business days and to the FDA within 10 business days.

In contrast to a UADE, an anticipated SAE is any SAE, the nature or severity of which has been reported in clinical trials of the Control-IQ System, or reported to Tandem Diabetes Care, Inc. by users of the t:slim X2 insulin pump. AEs reported during clinical studies of the Control-IQ system and post-market vigilance of the t:slim X2 insulin pump include, but are not limited to, the events shown below. The following device issues are anticipated and will not be reported on a Device Issue Form but will be reported as an Adverse Event if the criteria for AE reporting described above are met:

- Component disconnections
- CGM sensors lasting fewer than the number of days expected per CGM labeling
- CGM tape adherence issues
- Pump infusion set occlusion not leading to ketosis
- Battery lifespan deficiency due to inadequate charging or extensive wireless communication
- Intermittent device component disconnections/communication failures not leading to system replacement
- Device issues clearly addressed in the user guide manual that do not require additional troubleshooting
- Skin reactions from CGM sensor placement or pump infusion set placement that do not meet criteria for AE reporting

In addition, if the device issue is listed in Tandem Procedure QS-045, FDA Medical Device Reporting will be anticipated and not reported on a Device Issue Form. Any other device-related SAE will be considered an unanticipated adverse device event (UADE).

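### The protocol's rule for an anticipated SAE conflicts with its own UADE definition, so some device-related SAEs can lose the UADE label and its 5-business-day IRB report

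*Combined protocol and SAP*

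**What the plan says.** Both rules stand in the section Unanticipated Adverse Device Effect (UADE).

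- **UADE definition.** A serious device effect qualifies if it was "not previously identified in nature, severity, or degree of incidence in the risk assessment, the ICF as well as the protocol". A catch-all for other unanticipated serious problems associated with a device follows. The protocol presents this definition as following 21 CFR Part 812.
- **Anticipated SAE.** The next paragraph, introduced as a contrast to the UADE, says that "an anticipated SAE is any SAE, the nature or severity of which has been reported in clinical trials of the Control-IQ System". The sentence then accepts a second source on equal terms, namely earlier complaints that pump customers have made to the sponsor.
- **Residual sentence.** After a list of anticipated device issues and a reference to a company procedure, the section ends: "Any other device-related SAE will be considered an unanticipated adverse device event (UADE)".
- **Clocks.** "An unanticipated device effect must be reported to the IRB within 5 business days and to the FDA within 10 business days". Separately, under Serious Adverse Event (SAE): "A serious adverse event must be reported to the FDA as soon as possible, within a maximum of 15 calendar days".

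The classification is used in practice. Under Adverse Event Definitions, anticipated or unanticipated is a field on the adverse event form, and the investigator settles it in order to establish what reporting is required.

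**The concern.** The anticipated-SAE sentence is meant to be the other side of the UADE definition, but it is not its complement. It accepts a match on nature or on severity alone, it does not mention incidence, and it replaces three named documents with earlier trial or user reports. Some events therefore fall into both classes, and two investigators who both follow the section could classify the same event in opposite ways.

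What is at stake is which reporting clock starts. The omitted attribute also matters for this study in particular. Its primary objective is the rate of severe hypoglycemia (SH) and diabetic ketoacidosis (DKA), both known event types, so a change in their frequency is the kind of novelty that the anticipated-SAE sentence cannot register.

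**Working it through.** There is no plan figure to reproduce. The check compares the two rules and then the reporting clocks.

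**Step 1: the rules by attribute.** The UADE definition is read so that one new attribute is enough. The event is a device-related SAE.

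| Nature | Severity | Incidence | UADE definition | Anticipated-SAE sentence | Result |
|---|---|---|---|---|---|
| known | new | any | UADE | anticipated | conflict |
| known | known | new | UADE | anticipated | conflict |
| new | known | any | UADE | anticipated | conflict |
| new | new | any | UADE | not anticipated | agree |
| known | known | known | not a UADE | anticipated | agree |

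The third row is the least obvious. Taken literally, a new kind of event counts as anticipated if its severity has been reported before.

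**Step 2: how far this depends on the reading.** The definition could instead be read as requiring all three attributes to be new. The three conflicts would then disappear. That reading is hard to sustain: an event of a wholly new kind has no known severity or incidence, so naming those two attributes would add nothing.

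**Step 3: the reference sources.** The definition looks to the risk assessment, the consent form and the protocol. The anticipated-SAE sentence looks to Control-IQ trials and to reports from t:slim X2 users. It sets no time limit and does not require that Control-IQ was in use. Study participants are themselves t:slim X2 users (Initiation of therapy with the Control-IQ System), so, read literally, a first report within the study could make the next such event anticipated. This mismatch remains under either reading in Step 2.

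**Step 4: the clocks.** Business days were converted to calendar days by counting from each day of the week.

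| Limit | No holiday | One assumed holiday |
|---|---|---|
| UADE to IRB, 5 business days | 5 to 7 calendar days | 5 to 10 |
| UADE to FDA, 10 business days | 12 to 14 calendar days (14 from any weekday) | 12 to 17 |
| Any SAE to FDA | 15 calendar days | 15 |

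If an event loses the UADE label, its FDA limit moves from 12–14 to 15 calendar days: 15 − 14 = 1 and 15 − 12 = 3, so 1 to 3 days later without a holiday. With one holiday the SAE limit can fall up to 17 − 15 = 2 days earlier than the UADE limit. For the IRB, a limit of 5 to 7 calendar days is replaced by none. Under Institutional approval of the protocol, the investigator keeps the IRB informed of SAEs and UADEs, but no deadline is given.

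**The case against.** The strongest reply is that little turns on the label. The 15-day FDA rule makes no exception for anticipated SAEs. The section Expedited Safety Reports applies 21 CFR 803 reporting to all adverse events in the study. The IRB is kept informed of SAEs. SH and DKA incidence is queried monthly in the surveillance database (Observation and Recording of Adverse Events), and outcomes are analyzed quarterly (Statistical Considerations). All of this stands. A reader might infer that such events escape expedited reporting, or that a rising SH or DKA rate would go unseen. The documents do not support either inference.

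A reader might also multiply the benchmark SH and DKA rates by the expected number of completers and treat the product as the number of misclassified events. That does not follow. A UADE must be serious and device-related, SH as defined is not automatically an SAE, and relatedness is judged event by event. Moreover, events occurring at the benchmark rate are not new in incidence under either rule.

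It can further be said that the text sets no order of precedence. The definition is tied to Part 812, to which the study commits under Good Clinical Practice/Regulatory Compliance, and it carries its own catch-all. The residual sentence directly follows the device-issue list and the company procedure, so it is unclear what it is residual to. This also stands: it cannot be said that the looser rule governs, only that it can be read that way. An unresolved precedence is itself a reason to amend.

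Finally, the risk assessment, the consent form text and the company procedure were not available for this review. They may already identify some severities or frequencies, which would make the two rules agree more often in practice.

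**Conclusion.** The two rules conflict and need to be reconciled. Followed as written, the anticipated-SAE sentence can remove the UADE label from a device-related SAE that meets the protocol's own definition. The loss is mainly the 5-business-day IRB report, and secondarily the 10-business-day FDA clock, whose practical effect is about 1 to 3 calendar days when no holiday intervenes. FDA reporting of SAEs, device reporting and undated notice to the IRB all remain.

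The attribute conflict rests on the reading that one new attribute is enough; the mismatch in reference sources does not. The number of events affected cannot be estimated, because the documents give neither a device-related fraction nor the severities and incidences already identified. The point concerns safety classification and reporting time. It does not affect the primary analysis.

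**What to change.** Amend the section Unanticipated Adverse Device Effect (UADE) in two places.

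1. Define an anticipated SAE as the exact complement of the UADE definition: its nature, its severity and its degree of incidence have all been previously identified, judged against the same documents (risk assessment, consent form and protocol).
2. State that this definition governs the closing sentence on other device-related SAEs, so that precedence is clear.

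This is a short wording change. It alters no endpoint, sample size or analysis. The cost is that a few more events will need expedited assessment.

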**Relationship of Adverse Event to Study Device (causality):**

The clinical investigator will assess the relationship of any adverse event to be related or unrelated by determining if there is a reasonable possibility that the adverse event may have been caused by the study device. To ensure consistency of adverse event causality assessments, the investigator will apply the following guidelines when determining whether an adverse event is related:

**YES:** There is a plausible temporal relationship between the onset of the adverse event and the study intervention, and the adverse event cannot be readily explained by the subject's clinical state, intercurrent illness or concomitant therapies; and/or the adverse event follows a known pattern of response to the study intervention; and/or the adverse event abates or resolves upon discontinuation of the study intervention.

**NO:** Evidence exists that the adverse event has an etiology other than the study intervention (e.g., preexisting medical condition, underlying disease, intercurrent illness, or concomitant medication); and/or the adverse event has no plausible temporal relationship to study intervention.

**Adverse Device Effect (ADE):**

Any untoward medical occurrence in a study subject which the device may have caused or to which the device may have contributed (Note that a Device Deficiency or Issue Form must be completed in addition to an Adverse Event Form, if the event is determined to be an ADE).

**Intensity of Adverse Event:**

The intensity of an adverse event will be rated on a three-point scale: 1) mild, 2) moderate, or 3) severe. The term severe is a measure of intensity: thus, a severe adverse event is not necessarily serious. For example, itching for several days may be rated as severe, but may not be clinically serious.

- Mild: Usually transient, requires no special treatment, and does not interfere with the subject's daily activities.
- Moderate: Usually causes a low level of inconvenience or concern to the subject and may interfere with daily activities but is usually ameliorated by simple therapeutic measures.
- Severe: Interrupts a subject's usual daily activities and generally requires systemic drug therapy or other treatment.

**Expedited Safety Reports:**

As the Control-IQ System is an FDA-approved and commercially available product in the US, in addition to SH, DKA, SAEs and UADEs, medical device reporting requirements (21 CFR 803) are applicable to all AEs reported through this study.

## **STATISTICAL CONSIDERATIONS**

### **Determination of Sample Size**

The approach to sample size and statistical analyses are summarized below. A detailed statistical analysis plan will be written and finalized prior to the first tabulation of data. In order to determine the incidence rates on which the power analyses were based, Tandem conducted a literature review (see Attachment 1 for methodology). Ranges of event rates reported in the literature for both severe hypo and DKA in patients with T1D are very broad; 0-100 events/100PY for severe hypoglycemia, and 0.4 – 26 events/100 PY for DKA (see Table 1, Attachment 1). Therefore, for purposes of power analyses for the proposed study, we used event rates from a recently published study using a large Type 1 Diabetes Exchange cohort (Foster et al, 2019). This study used a similar design as our approved post-market study, the subjects represent our intended use population, and the event rates reported in the Foster study fall within the broader rates found in the extensive body of literature reviewed.

Sample size was determined in 3 steps:

#### *Step 1 – Power analysis for severe hypoglycemia (SH)*

An overall incidence rate of 25.35 events per 100 patient years (PY) was used in the power analysis for severe hypoglycemia. We calculated that a sample size of 1,354 individuals with T1D would provide 80% power with a type 1 error rate (two-sided) of 5% to detect a difference, if there is one, between the expected SH rate (25.35) and the proposed study sample SH event rate.

A separate power analysis for the 14-18 age group used an overall SH incidence rate of 19.5 events/100PY. Results indicated that a sample size of 231 individuals with T1D between the ages of 14-18 would provide 80% power with a type 1 error rate (two-sided) of 5% to detect a difference, if there is one, between the expected SH rate (19.5) and the proposed study sample SH event rate. Of the overall sample of 1,354 subjects, at least 231 subjects will be 14-18 years old to provide sufficient power to detect risk of SH in this younger age group.

A separate power analysis for the 6-13 year old group used a SH incidence rate of 21.9 events/100PY, which is a weighted average of both MDI and pump users (since pump users were overrepresented in this age group). Results indicated that a sample size of 288 individuals with T1D between the ages of 6 and 13 would provide 80% power with a type 1 error rate (two-sided) of 5% to detect a difference, if there is one, between the expected SH rate (21.9) and the proposed study sample SH event rate. In addition to

the overall sample, at least 288 subjects will be 6-13 years old to provide sufficient power to detect risk of SH in this younger age group. *Step 2 – Power analysis for diabetic ketoacidosis (DKA)*

An overall incidence rate of 11.03 events per 100 patient years was used in the power analysis for DKA . We calculated that a sample size of 1,282 individuals with T1D would provide 80% power with a type 1 error rate (two-sided) of 5% to detect a difference, if there is one, between the expected DKA rate (11.03/100 PY) and the proposed study sample DKA event rate.

A separate power analysis for the 14-18 age group used an overall DKA incidence rate of 14.2 events/100PY. Results indicated that a sample size of 328 individuals with T1D between the ages of 14-18 would provide 80% power with a type 1 error rate (two-sided) of 5% to detect a difference, if there is one, between the expected DKA rate (14.2) and the proposed study sample DKA event rate. Of the overall sample of 1,282 subjects, at least 328 subjects will be 14-18 years old to provide sufficient power to detect risk of DKA in this younger age group.

A separate power analysis for the 6-13 year old group used an overall DKA incidence rate of 13.2 events/100PY, which is a weighted average of both MDI and pump users (since pump users were overrepresented in this age group). Results indicated that a sample size of 77 individuals with T1D between the ages of 6-13 would provide 80% power with a type 1 error rate (two-sided) of 5% to detect a difference, if there is one, between the expected DKA rate (13.2/100PY) and the proposed study sample DKA event rate. In addition to the previously determined sample, at least 77 subjects will be 6-13 years old to provide sufficient power to detect risk of DKA in this younger age group.

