### Data Collection:

The data will be collected per the schedule outlined below:

Procedure/Assessment	Baseline*	Monthly	Months 3 and 6	Final
Informed Consent	X			
**Release of Medical Records				
Screening for eligibility	X			
Report of incoming AEs		X		X
Outreach for AEs	X	X		X
User Experience	X		X	X

Psychosocial Outcomes	X	X	X
-----------------------	---	---	---

\*Includes demographics, frequency of AEs

\*\*Only requested as needed to collect additional information on reported AEs

Investigators will be provided a process for assigning a de-identified number to the subject and will be required to keep any study paperwork or electronic files in a secure private area. Electronic audits will be in place to help ensure that data entered is within reasonable limits.

**Informed Consent Process:** All subjects must electronically sign the ICF (see **APPENDIX B**) approved by the IRB to be enrolled in the study. The subject will receive study team contact information (email and telephone) and be given ample opportunities to ask questions about the procedures, required schedule of data collection, and the benefits and risks of participating in the study before signing the ICF. All subjects will receive an electronic copy of the ICF to keep for their records. Subjects will be informed of any revisions to the ICF and any revisions must be electronically signed and kept in the subject study file. In addition, a signed Release of Medical Records form may be obtained if needed to collect additional information on reported Adverse Events to allow the investigators to obtain accurate event information when necessary. Acquisition of the informed consent, Release of Medical Records form (if applicable) and any revisions will be documented in the survey database.

**Demographics:** The following demographic data will be obtained: date of birth, gender, race, ethnicity, educational level, socioeconomic status, residence, employment status, weight, height, and type of health insurance.

**Medical History:** Medical history, including existing comorbidities deemed clinically relevant (e.g. retinopathy, nephropathy, neuropathy, history of cardiovascular events) will be collected at baseline. In addition, details specific to type 1 diabetes, including age at diagnosis, duration of disease, previous therapy, most recent HbA1c within the past 6 months, frequency of SH and DKA, and family history will be collected from the study subject in the baseline questionnaire.

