## **Statistical Analysis**

Descriptive statistics will be used to describe outcomes vs. a comparator group. The Comparator Group will be determined using evidence from a systematic literature review examining MDI, insulin pump therapy (IPT) and sensor augmented pump (SAP) use in patients with type 1 diabetes. Studies published since January, 2020 will be included in the analysis. This will establish the baseline sample representation and outcome metrics. Users of automated dosing systems, including low glucose suspend, predictive low glucose suspend (such as Basal-IQ technology) will not be analyzed as part of the Comparator group.

The publications included in the literature review have been identified to represent the typical population of people with type 1 diabetes, and include sample populations that mirror those described above in the target population for this study, including:

- Children age 6 years old and older
- Adolescents age 14-18 years old
- Adults >18 years old
- Patients with pump experience
- Pump naïve patients
- Patients with CGM experience
- CGM naïve patients
- Wide range of baseline HbA1c values

Primary endpoints, the risk of AE (DKA, SH), represented as risk ratio per 100 patient years, will be compared using a single sample two-tailed exact binomial test (alpha=0.05) to the expected values as extracted in the literature review. Effect size will be defined as the absolute difference in risk ratios.

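### The expected SH and DKA rates for the 14-18 and 6-13 cohorts are those of bands one year younger (13-17 and 6-12), so the 14-18 comparison does not set like against like

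*Combined protocol and SAP*

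**What the plan says.** Step 1 of Determination of Sample Size gives the adolescent SH reference: "A separate power analysis for the 14-18 age group used an overall SH incidence rate of 19.5 events/100PY". It concludes that "a sample size of 231 individuals with T1D between the ages of 14-18" is enough. Step 2 does the same for DKA: "A separate power analysis for the 14-18 age group used an overall DKA incidence rate of 14.2 events/100PY", leading to "a sample size of 328 individuals with T1D between the ages of 14-18". For the younger cohort, "A separate power analysis for the 6-13 year old group used a SH incidence rate of 21.9 events/100PY", with 13.2 for DKA in Step 2.

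The synopsis and Step 3 define the recruitment cohorts as 6 to 13, 14 to ≤18, and >18. The table under Primary Outcome gives its age-specific rates for ages 6-12, 13-17 and 18-93. The Statistical Analysis section says that the publications reviewed include samples mirroring the target population, and lists adolescents of 14-18 and adults over 18 among them. No section states which table band serves which cohort, or adjusts for the shift.

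The success goal under Primary Outcome is worded for overall outcomes. The Demographics paragraph confirms that age can be computed exactly: "The following demographic data will be obtained: date of birth".

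**The concern.** The largest step between the table's age bands is at 18, where SH rises from 20 to 30 and DKA falls from 14 to 9 per 100 PY. The study puts 18-year-olds on the adolescent side of that step, while the source of the reference rates puts them on the adult side. It also takes 13-year-olds out of the adolescent group, where the source has them.

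The 14-18 cohort has its own two-sided power statements for both primary safety events, and its DKA calculation sets the quota of 328. If the cohort's observed rates are set against 19.5 and 14.2, part of any difference reflects who is in each band rather than the device. On the table's adult figures this would tend to suggest an SH excess that is not there and to make a DKA excess harder to see.

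**Working it through.** **The plan's own figures.** The 231 and 328 cannot be reproduced, because no alternative rate is given. Solving the usual one-sample binomial formula backwards (two-sided 5%, 80% power), 231 at 19.5 implies an alternative of 12.6 or 27.1, and 328 at 14.2 implies 9.1 or 19.8. The lower values round to the table's pump-user rates for ages 13-17 (13 and 9), which fits a 13-17 source without proving it. The missing alternative is a separate gap.

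**Matching cohorts to bands** (all insulin delivery, per 100 PY).

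| Study cohort | Planning rate SH / DKA | Table band | Table rate SH / DKA |
|---|---|---|---|
| 6-13 | 21.9 / 13.2 | 6-12 | 22 / 13 |
| 14 to ≤18 | 19.5 / 14.2 | 13-17 | 20 / 14 |
| >18 | none given | 18-93 | 30 / 9 |

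All four planning rates round to the table value of the younger band.

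**Size in the 14-18 cohort.** Let w be the share of 18-year-olds. It is not in the documents; 20% is one of five single-year ages. Assume for illustration that they carry the 18-93 rates.

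- SH = (1−w)×19.5 + w×30. At w = 0.1, 0.2, 0.3 this is 20.6, 21.6, 22.7 (+5%, +11%, +16%).
- DKA = (1−w)×14.2 + w×9. This is 13.7, 13.2, 12.6 (−4%, −7%, −11%).
- The band also swaps out 13-year-olds. If they carry the 6-12 rate and are a fifth of the 13-17 band, SH is 19.5 − 0.2×21.9 + 0.2×30 = 21.1 and DKA is 14.2 − 0.2×13.2 + 0.2×9 = 13.4. The signs do not change.

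**Chance of a significantly higher result with no device effect.** Find the smallest count whose upper tail under the reference rate is at most 2.5%, then take its probability under the blended rate. Two person-time figures are used: 328 PY (the full quota) and 0.75 × 328 = 246 PY (completers after the stated 25% attrition). Each pair below is exact Poisson, then the plan's exact binomial test.

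| Event and scenario | 328 PY | 246 PY |
|---|---|---|
| SH, no band shift | 2.2%, 2.4% | 2.1%, 2.4% |
| SH, w = 10%, age-18 rate 30 | 5.9%, 6.7% | 5.0%, 6.1% |
| SH, w = 20%, age-18 rate 30 | 12.7%, 15.2% | 10.2%, 12.8% |
| SH, w = 20%, age-18 rate 25 (blend 20.6) | 6.1%, 7.0% | 5.2%, 6.3% |
| SH, w = 20%, age-18 rate 22 (blend 20.0) | 3.6%, 4.0% | 3.3%, 3.8% |
| DKA, no band shift | 2.4%, 2.3% | 2.1%, 2.0% |
| DKA, w = 20%, age-18 rate 9 | 0.6%, 0.5% | 0.6%, 0.5% |

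At w = 30% and 328 PY, the SH figures are 23% and 29%.

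**6-13 cohort.** With 13-year-olds as one of eight ages (12.5%) at the 13-17 rate, SH is 0.875×21.9 + 0.125×19.5 = 21.6 against 21.9. DKA is 0.875×13.2 + 0.125×14.2 = 13.3 against 13.2. Both shifts are under 2%.

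**The case against.** Four points can fairly be made against this.

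1. *No cohort-level criterion.* A reader might infer that the 14-18 cohort passes or fails against 19.5 and 14.2. The documents do not say so. Success is worded for overall outcomes, and these rates appear only as expected values in power analyses. This stands. What remains is that the plan sizes the cohort to detect a difference from exactly these rates and prints age-specific columns beside its goal, so the comparison is likely to be made and read.

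2. *Direction assumed.* A reader might also infer that the two references are off in opposite directions as a matter of fact. That needs 18-year-olds to carry the average rate of a band that runs to age 93. Every adult delivery row agrees in sign (SH 27 to 38, all above 19.5; DKA 7 to 13, all below 14.2), but no row is specific to age 18. If their SH rate were 19.5, there would be no SH shift.

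3. *Delivery mix can outweigh age, notably for DKA.* Step 3 seeks equal numbers of pump users and pump-naïve subjects above 14. If adolescents had a 50:50 mix of the table's MDI and pump rates, DKA would be (25+9)/2 = 17 at 13-17 and (13+7)/2 = 10 in adults. At a 20% share the blend is 0.8×17 + 0.2×10 = 15.6, which is above 14.2. The DKA direction can therefore reverse.

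4. *The age cut is ambiguous.* Read as exact age, ≤18 would send someone aged 18.5 to the adult cohort, and almost no 18-year-olds would remain in the adolescent one. Completed years is the more natural reading, since exact age would leave someone aged 13.5 between the 6-13 and 14-18 cohorts. The plan should still say which is meant.

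**Conclusion.** The mismatch holds: the cohort reference rates match table bands one year younger than the cohorts, and age 18 lies on opposite sides of the adult boundary in the study and in its source. The mapping is inferred from four rates that agree after rounding. It conflicts with the plan's statement that the literature samples mirror its cohorts.

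The size is conditional. With 18-year-olds at the 18-93 rate and a 20% share, a significantly higher SH result with no device effect has a chance of about 13-15% at 328 PY or 10-13% at 246 PY, against about 2%. It drops to 5-7% at a 10% share or at an age-18 rate of 25, and to 3-4% at a rate of 22. For DKA the chance falls to about 0.5%, but the delivery mix could reverse that direction.

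The documents support neither a failed 14-18 criterion nor an established bias in opposite directions. They do support an unstated lack of comparability in a planned safety comparison, which is cheap to remove. The 6-13 cohort does not need it on grounds of size.

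**What to change.** Keep the recruitment quotas. In the detailed SAP, which is still to be finalized, do one of the following:

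- make the age-specific benchmark comparisons in the table's own bands (6-12, 13-17, 18 and over), with age computed from date of birth; or
- keep the cohorts and give each an expected count: the sum over participants of patient-time multiplied by the rate of the table band that contains the participant's age.

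Neither needs a rate at age 18. Restate the reference rates in Steps 1 and 2 to match, and say that the age cut is in completed years.

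The cost is wording only, with no new data or subjects. The small downside of the first option is that analysis bands no longer equal quota bands. With equal single-year shares, the 13-17 band would hold about 328 − 0.2×328 + 0.125×385 ≈ 310 recruits instead of 328. The second option leaves cohort sizes unchanged.
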